Appendix 1 Schedule of Activities (cont.)

	Screen Visit ^a	Run-In Visit ^b	Double-Blind Treatment Period: Treatment Every 28 (±N) Days ^c															Safety Follow-Up Period		ET Visit ^c	UV ^d	
			Pre-Rand.	Post-Rand.	4	6	10	14	18	22	26	30	34	38	42	46	50	54	62			70
Week	-4 to -2	0	2		4	6	10	14	18	22	26	30	34	38	42	46	50	54	62	70	-	-
(Visit Window in Days) ^e				(±3)	(±5)	(±5)	(±5)	(±5)	(±5)	(±5)	(±5)	(±5)	(±5)	(±5)	(±5)	(±5)	(±5)	(±5)	(±14)	(±14)	-	-
Visit	1	2	3		4	5	6	7	8	9	10	11	12	13	14	15	16	17	18	19	-	-
Hematology ^u	x	x		x	x	x	x	x	x	x	x	x	x	x	x	x	x	x		x	x	
Chemistry ^v	x			x	x	x	x	x	x	x	x	x	x	x	x	x	x	x		x	x	
Fasting lipids & glucose ^{w,x}		x			x												x		x	x		
HbA _{1c}	x				x												x		x	x		
Hepatitis B & C serologies ^y	x																					
Quantitative hepatitis C RNA PCR ^z	x																					
Hepatitis B DNA ^{aa}	x						x							x								
Urinalysis ^{bb}	x			x						x							x		x	x		
Serum specific IgE				x																		
PK sample (all patients) ^{l, cc}				x	x	x	x			x			x			x	x		x	x		
Additional PK samples (selected sites/patients)			See Appendix 2																			
Anti-drug antibodies				x			x			x			x				x		x	x		
Plasma and serum samples for biomarker analysis		x		x	x		x	x			x			x			x		x	x		x

Appendix 1 Schedule of Activities (cont.)

	Screen Visit ^a	Run-In Visit ^b	Double-Blind Treatment Period: Treatment Every 28 (±N) Days ^c															Safety Follow-Up Period		ET Visit ^c	UV ^d	
			Pre-Rand.	Post-Rand.	4	6	10	14	18	22	26	30	34	38	42	46	50	54	62			70
Week	-4 to -2	0	2		4	6	10	14	18	22	26	30	34	38	42	46	50	54	62	70	-	-
(Visit Window in Days) ^e				(±3)	(±5)	(±5)	(±5)	(±5)	(±5)	(±5)	(±5)	(±5)	(±5)	(±5)	(±5)	(±5)	(±5)	(±5)	(±14)	(±14)	-	-
Visit	1	2	3		4	5	6	7	8	9	10	11	12	13	14	15	16	17	18	19	-	-
Urine sample for biomarker analysis		x		x	x			x			x							x				x ^{dd}
Blood sample for RNA analysis (PAXgene tube)				x														x				x
Blood sample for specified DNA SNP analysis ^{ee}				x																		
Blood sample for RBR (DNA WGS) (optional, if applicable to site) ^{ff}				x																		
Single-blind study drug (placebo) administration ^{gg}		x																				
Study drug administration (MSTT1041A or placebo) ^{hh}				x ^{gg}		x ^{gg}	x ^{gg}	x ^{gg}	x ^{gg}	x	x	x	x	x	x	x	x					
Concomitant medications ⁱⁱ	x	x	x		x	x	x	x	x	x	x	x	x	x	x	x	x	x	x	x	x	x
Adverse events ^{jj}	x	x	x	x	x	x	x	x	x	x	x	x	x	x	x	x	x	x	x	x	x	x

Appendix 1 Schedule of Activities (cont.)

ACQ = Asthma Control Questionnaire; ACQ-7 = Asthma Control Questionnaire (7 items); ACQ-5 = Asthma Control Questionnaire (5 items); AQLQ = Asthma Quality-of-Life Questionnaire; BMI = body mass index; CGIC = Clinician Global Impression of Change; CT = computed tomography; ECG = electrocardiogram; eCRF = electronic case report form; eDiary = electronic Diary; EoS = End-of-Study; ET = early termination; EQ-5D = EuroQol 5-Dimension Questionnaire; FeNO = fractional exhaled nitric oxide; HbA1c = hemoglobin A1c; HbsAg = hepatitis B surface antigen; HbsAb = hepatitis B surface antibody; HbcAb = hepatitis B core antibody; HCV = hepatitis C virus; IgE = Immunoglobulin E; PCR = polymerase chain reaction; PGIC = Patient Global Impression of Change; PK = pharmacokinetic; PPD = purified protein derivative; PRO = patient-reported outcome; Q4W = every 4 weeks; QFT = QuantiFERON[®] test; Rand. = randomization; RBR = Roche Biosample Repository; SC = subcutaneous; Screen = screening; SGRQ = St. George's Respiratory Questionnaire; TB = tuberculosis; UV = unscheduled visit; WGS = whole genome sequencing.

Notes: On treatment days, all assessments should be performed prior to dosing, unless otherwise specified.

Patients who are unable to tolerate study drug will discontinue study drug but should continue follow-up for all other study procedures and measurements through the end of the study.

^a The screening period may be between 12 and 28 days after study consent, as described in Section 4.5.2.

^b The run-in visit should be scheduled 2 weeks (± 5 days) prior to the randomization visit.

^c Patients who are randomly allocated into the 52-week double-blind treatment period but discontinue study drug should continue follow-up for all other study procedures and measurements through the end of the study. Patients who discontinue from the study prior to Week 50 should return to the site for an early termination visit 4 weeks (± 5 days) after the last dose of study drug and then enter the safety follow-up period.

^d Patients who experience symptoms consistent with an asthma exacerbation as defined in Appendix 12 will be asked to come to the clinic for an unscheduled visit. Patients will be asked to bring a urine sample and will undergo additional evaluations.

^e Visit windows are relative to randomization visit.

^f Atopy status (atopic or non-atopic) will be assessed on the basis of historical documentation (e.g., patient's medical records), as described in Section 4.5.4.

^g PRO questionnaires will be completed before the patient receives any information on disease status, prior to the performance of other site-visit assessments and procedures, and prior to the administration of study treatment. Both the full (7 items) and 5 item (ACQ-5) version of the ACQ will be administered in this study. The ACQ-5 is part of the eligibility criteria and will be administered at screening and run-in visits. The full ACQ-7 will be administered at the remaining timepoints as indicated in the Schedule of Activities (randomization visit, Week 26, and Week 54).

^h Clinicians will complete the CGIC after they have examined the patient and evaluated data that support an overall health assessment, which may include, but are not limited to, FEV₁, FeNO, and medical records.

ⁱ Includes evaluation of the head, eyes, ears, nose, and throat, and the cardiovascular, dermatological, musculoskeletal, respiratory, gastrointestinal, and neurological systems. Record abnormalities observed prior to dosing at Visit 2 on the General Medical History and Baseline Conditions eCRF. At subsequent visits, record new or worsened clinically significant abnormalities on the Adverse Event eCRF.

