3. STUDY DESIGN

3.1 DESCRIPTION OF THE STUDY

3.1.1 Overview of Study Design

This is a Phase IIb, randomized, placebo-controlled, double-blind, multicenter, multi-arm study of MSTT1041A compared with placebo as add-on therapy in patients with severe, uncontrolled asthma who are receiving medium- or high-dose ICS therapy and at least one of the following additional controller medications: LABA, leukotriene modifier (LTM), long-acting muscarinic antagonist (LAMA), or long-acting theophylline preparation. Patients must have evidence of uncontrolled disease consisting of an Asthma Control Questionnaire–five items (ACQ-5) score of ≥ 1.5 and at least one symptom of asthma that is not controlled *during each of 2 consecutive weeks* (nighttime awakening ≥ 1 time/week and/or short-acting rescue therapy use > 2 days/week). Patients requiring use of systemic corticosteroids (oral, IV, or intramuscular [IM]) or biologic therapy (e.g., anti-IgE or anti-IL-5) at screening will be excluded from the study.

The study will consist of a 2- to 4-week screening period, a 2-week single-blind placebo run-in period, a 52-week double-blind treatment period, and a 16-week follow-up period concluding at the end-of-study (EOS) visit at Week 70.

At screening, patients must demonstrate acceptable inhaler, peak flow meter, and spirometry techniques. During the screening period, patients must demonstrate compliance with required daily use of an electronic device (eDiary) for documenting asthma controller medication use and answering questions related to asthma symptoms, nighttime awakenings due to asthma, and use of short-acting rescue therapy; compliance with daily measurement of peak expiratory flow rate (PEFR); and adherence to their usual asthma controller medication regimen (ICS plus at least one additional controller medication), as recorded daily in the eDiary (see Section 4.1.1 for details).

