Patients who fail to meet eligibility criteria during the screening period will be permitted to re-screen twice for selected reasons, as described in Section 4.5.2. At the run-in visit (Week 0), scheduled for approximately 2 weeks prior to the randomization visit (Week 2), patients who meet enrollment criteria for the run-in period will receive one single-blind dose of placebo to allow for evaluation of unexpected variability in asthma control. At the randomization visit, patients will undergo further assessments to determine eligibility for randomization to the double-blind treatment period. Patients who experience unexpected variability in asthma control, as demonstrated by change in forced expiratory volume in 1 second (FEV₁) and/or fractional exhaled nitric oxide (FeNO) will not be eligible for double-blind treatment (see Section 3.3.4).

[figure not shown]
A total of approximately 500 patients will be randomized in a 1:1:1:1 ratio to receive MSTT1041A at one of three doses (70 mg, 210 mg, or 490 mg) or placebo, stratified by blood eosinophil status at Visit 1 (< 150, ≥ 150 to < 300, ≥ 300 cells/μL), number of *documented* asthma exacerbations (*as defined in Appendix 12*) in the previous 12 months (1–2, ≥ 3), total daily ICS dose at Visit 1 (< 1000 μg, ≥ 1000 μg of fluticasone proportionate or equivalent), and country. Enrollment caps will be utilized to ensure adequate power for biomarker subgroup analysis based upon blood eosinophil status at Visit 1 (≥ 300, < 300 cells/μL). The randomization will be such that approximately 30 patients per arm will have eosinophil-high status and approximately 95 patients per arm will have eosinophil-low status. Study drug will be administered as four SC abdominal injections at the randomization visit (Week 2), Week 6, and every 4 weeks (Q4W) thereafter through Week 50.

Daily measurement of PEFR and daily assessment of asthma symptoms, nighttime awakenings due to asthma, and use of short-acting rescue therapy will be performed at home. More detailed assessments, including spirometry, FeNO measurements, and patient-reported outcome assessments, will be performed during scheduled site visits. All patients will undergo pharmacokinetic (PK), biomarker, and ADA sampling. Additional PK samples will be collected at prespecified timepoints for characterization of

absorption and accumulation of MSTT1041A in approximately 80 patients who consent to this option (see Appendix 2).

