- For women of childbearing potential: agreement to remain abstinent (refrain from heterosexual intercourse) or use a contraceptive method with a failure rate of $< 1\%$ per year during the treatment period and for at least 20 weeks after the last dose of study drug

A woman is considered to be of childbearing potential if she is postmenarcheal, has not reached a postmenopausal state (≥ 12 continuous months of amenorrhea with no identified cause other than menopause), and has not undergone surgical sterilization (removal of ovaries and/or uterus).

Examples of contraceptive methods with a failure rate of $< 1\%$ per year include bilateral tubal ligation, male sterilization, hormonal contraceptives that inhibit ovulation, hormone-releasing intrauterine devices, and copper intrauterine devices.

The reliability of sexual abstinence should be evaluated in relation to the duration of the clinical trial and the preferred and usual lifestyle of the patient. Periodic abstinence (e.g., calendar, ovulation, symptothermal, or postovulation methods) and withdrawal are not acceptable methods of contraception.

- For men: agreement to remain abstinent (refrain from heterosexual intercourse) or use a condom, and agreement to refrain from donating sperm, as defined below:

With female partners of childbearing potential or pregnant female partners, men must remain abstinent or use a condom during the treatment period and for at least 20 weeks after the last dose of study drug to avoid exposing the embryo. Men must refrain from donating sperm during this same period.

The reliability of sexual abstinence should be evaluated in relation to the duration of the clinical trial and the preferred and usual lifestyle of the patient. Periodic abstinence (e.g., calendar, ovulation, symptothermal, or postovulation methods) and withdrawal are not acceptable methods of contraception.

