4.5.12.1 Pre-Bronchodilator Spirometry

Pre-bronchodilator spirometry evaluations should be performed in the morning, before use of bronchodilators. Asthma therapies that may affect spirometry must be withheld until pre-bronchodilator spirometry measurements are completed. Patients must be made aware that bronchodilator use is prohibited within a specified window prior to each clinic visit, with the exception of the screening visit or an unscheduled visit, as follows:

- Twice-daily LABA and twice-daily LAMA: prohibited within 12 hours prior to spirometry
- Once-daily LABA and once-daily LAMA: prohibited within 24 hours prior to spirometry
- SABA or SAMA: prohibited within 4 hours prior to spirometry

With the exception of an unscheduled visit, a patient's visit must be rescheduled if the patient arrives for a study visit having used a bronchodilator within the time window defined above for each medication. To accommodate the rescheduled visit, the usual visit window specified in the schedule of activities (see [Appendix 1](#)) may be extended to ± 4 days for Week 4 or ± 6 days for Week 6–54.

For safety reasons, consideration should be given to omitting spirometry if a patient is having an acute asthma exacerbation event at the time of the scheduled study visit.

Spirometric assessments will include FEV₁, forced vital capacity (FVC), percentage of predicted values for FEV₁ and FVC, FEV₁ to FVC ratio, and average expiratory flow during the middle portion of the expiration (FEF_{25–75}). The percentage of predicted values for FEV₁ and FVC will be derived from the third National and Nutrition Examinations Survey (Hankinson et al. 1999). Each test procedure requires that three valid spirometry maneuvers be performed within 1 hour. The highest FEV₁ and FVC values from the set of three accepted maneuvers will be recorded. Other parameters will be taken from the accepted maneuver with the highest sum of FEV₁ and FVC. A hard-copy report of the spirometry results will be maintained in the patient's medical record.

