5.3.1 Adverse Event Reporting Period

Investigators will seek information on adverse events at each patient contact. All adverse events, whether reported by the patient or noted by study personnel, will be recorded in the patient's medical record and on the Adverse Event eCRF.

MSTT1041A—Genentech, Inc.
72/Protocol GB39242, Version 4

Clinical Study Report: RO7187807 - Genentech, Inc.
Protocol GB39242 Report Number 1097359

After informed consent has been obtained **but prior to initiation of study drug**, only serious adverse events caused by a protocol-mandated intervention (e.g., invasive procedures such as biopsies, discontinuation of medications) should be reported (see Section 5.4.2 for instructions for reporting serious adverse events).

After initiation of study drug, *including for patients who discontinue study drug prematurely*, all adverse events will be reported until 20 weeks after the last dose of study drug *or until the last study visit, whichever is later*.

For patients who receive a placebo dose during the run-in period but are not randomly allocated, adverse events will be reported until 6 weeks after the placebo dose.

Instructions for reporting adverse events that occur after the adverse event reporting period are provided in Section 5.6.

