Appendix 1 Schedule of Activities

	Screen Visit ^a	Run-In Visit ^b			Double-Blind Treatment Period: Treatment Every 28 (±N) Days ^c														Safety Follow-Up Period		ET Visit ^c	UV ^d
			Pre-Rand.	Post-Rand.															Follow-Up Visit	EoS Visit		
Week	-4 to -2	0	2		4	6	10	14	18	22	26	30	34	38	42	46	50	54	62	70	-	-
(Visit Window in Days) ^e					(±3)	(±5)	(±5)	(±5)	(±5)	(±5)	(±5)	(±5)	(±5)	(±5)	(±5)	(±5)	(±5)	(±5)	(±14)	(±14)	-	-
Visit	1	2	3		4	5	6	7	8	9	10	11	12	13	14	15	16	17	18	19	-	-
Informed consent	x																					
Demographic data	x																					
Medical history and baseline conditions	x																					
Atopy status ^f	x																					
ACQ ^g	x	x	x								x							x				
PGIC ^g											x							x				
AQLQ(S) ^g			x								x							x				
SGRQ ^g			x								x							x				
EQ-5D-5L ^g			x															x				
CGIC ^h											x							x				
Complete physical examination ⁱ	x																					
Limited physical examination ⁱ			x								x							x		x	x	x
Weight (BMI) and height (height at screening only)	x																	x		x	x	
Vital signs ^k	x	x	x		x	x	x	x	x	x	x	x	x	x	x	x	x	x	x	x	x	x

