Eligible patients were randomized in a 1:1:1:1 ratio to receive MSTT1041A at one of three doses (70, 210, or 490 mg) or placebo. Enrollment caps were utilized to ensure adequate power for biomarker subgroup analysis based upon blood eosinophil status at visit 1 (≥ 300 , < 300 cells/ μ L). The randomization was conducted such that approximately 30 patients per arm will have eosinophil-high status and approximately 95 patients per arm will have eosinophil-low status. Study drug is administered as four SC abdominal injections at the randomization visit (Week 2), Week 6, and every 4 weeks thereafter through Week 50.

[figure not shown]
Safety and efficacy, as well as pharmacokinetic (PK) and pharmacodynamic (PD) measures, are assessed throughout the double-blind treatment period, as described in the protocol and detailed in the Schedule of Assessments (see [Appendix 2](#)). The primary efficacy endpoint is the incidence of asthma exacerbations during the 52-week double-blind treatment period (Week 2 through Week 54).

All patients will be followed for 20 weeks after the last dose of study treatment. The 20 weeks include 4 weeks after the final dose in the double-blind treatment period and 16 weeks in the safety follow-up period. Assessments for the safety follow-up period are detailed in the Schedule of Assessments (see [Appendix 2](#)).

All patients who discontinue study drug early during the double-blind treatment period are asked to continue with the study assessments in the double-blind treatment period and then complete the safety follow-up period. Patients who are unable or unwilling to continue with assessments in the double-blind treatment period complete an early termination visit and then enter the safety follow-up period.

The study design is depicted in [Figure 1](#).

Figure 1 Study Schema

ICS=inhaled corticosteroid; Q4W=every 4 weeks; SC=subcutaneous.

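### For patients dosed through Week 50, the end-of-study visit can fall in window 17.3 to 18.0 weeks after the last dose, short of the 20 weeks of follow-up stated in the SAP

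*Protocol*

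**What the plan says.** SAP Section 2 makes an unqualified statement: "All patients will be followed for 20 weeks after the last dose of study treatment". It then splits the 20 weeks into 4 weeks at the end of the double-blind period and 16 weeks of safety follow-up.

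Protocol 3.1.1 gives dosing as "every 4 weeks (Q4W) thereafter through Week 50" and describes "a 16-week follow-up period concluding at the end-of-study (EOS) visit at Week 70". In Appendix 1, the row headed "Visit Window in Days" shows ±5 days for Week 50 and ±14 days for Weeks 62 and 70. Footnote e fixes the reference point: "Visit windows are relative to randomization visit". The last dose is not the reference point for these windows.

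The same 20 weeks appears elsewhere in the protocol:

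- Section 5.3.1: "all adverse events will be reported until 20 weeks after the last dose of study drug", or until the last study visit if that comes later. Section 5.4.2.2 has the same rule for serious events and events of special interest.
- Sections 5.4.3.1 and 5.4.3.2: pregnancies in patients and in partners.
- Section 4.1.1.1, for men: abstinence or condom use "for at least 20 weeks after the last dose of study drug to avoid exposing the embryo".

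Appendix 1 shows no routine visit or contact after Week 70.

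**The concern.** The follow-up commitment is counted from the last dose, but the visit that closes follow-up is counted from randomization and may be two weeks early. Because the nominal interval is exactly 20 weeks, any early visit or late last dose that the other does not offset brings the final contact inside the 20 weeks. A site can do this without a protocol deviation.

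At stake is how safety information is collected late in the off-drug period. Protocol 5.3.1 has investigators seek adverse events at patient contacts, and none is scheduled after the end-of-study visit. Protocol 3.2 defines the end of the study by completed visits, so an early attender can count as complete while the reporting period is still open. The last hematology, chemistry, ECG, pregnancy test, pharmacokinetic and anti-drug antibody samples are also taken at this visit, and later spontaneous reporting cannot replace them. Incidence of anti-drug antibodies is a named safety endpoint (Protocol Section 2, SAP 2.1.4).

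**Working it through.** Count days from randomization, which is the Week 2 visit: day = 7 × (week − 2).

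**Inputs**
- Last scheduled dose, Week 50 (Protocol 3.1.1): 7 × 48 = day 336.
- Week 54: 7 × 52 = day 364.
- End-of-study visit, Week 70 (Protocol 3.1.1): 7 × 68 = day 476.
- End-of-study window: ±14 days from randomization (Appendix 1, footnote e), so days 462 to 490.
- Dosing window: ±5 days (Protocol 4.3.2.1; Appendix 1, Week 50).

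**The plan's own figure**
- Week 50 to 54: 364 − 336 = 28 days = 4 weeks.
- Week 54 to 70: 476 − 364 = 112 days = 16 weeks.
- Total: 476 − 336 = 140 days = 20.0 weeks.

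The SAP's 4 + 16 = 20 weeks reproduces exactly, with no slack.

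**Interval actually permitted**

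Interval = (476 + visit shift) − (336 + dose shift).

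| Last dose | Visit at −14 days | Visit on Week 70 | Visit at +14 days |
|---|---|---|---|
| 5 days early | 131 d (18.7 wk) | 145 d (20.7 wk) | 159 d (22.7 wk) |
| On time | 126 d (18.0 wk) | 140 d (20.0 wk) | 154 d (22.0 wk) |
| 5 days late | 121 d (17.3 wk) | 135 d (19.3 wk) | 149 d (21.3 wk) |

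At the early edge the shortfall is 140 − 126 = 14 days (14/140 = 10.0%) after an on-time dose, and 140 − 121 = 19 days (19/140 = 13.6%) after a dose 5 days late. With a dose 5 days late, even a visit exactly at Week 70 is 5 days short.

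**Who is affected**

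If the last dose was at Week 46 (day 308), the worst case is (476 − 14) − (308 + 5) = 149 days, which exceeds 140. For patients who stay on the visit schedule, the shortfall is therefore confined to those dosed at Week 50.

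**The case against.** The strongest reply is that SAP Section 2 describes the nominal design, which adds up, and that ±14 days is an ordinary symmetric tolerance. Visits may fall after 20 weeks as easily as before, and no section requires the final samples at 20 weeks or later. That stands as far as it goes: no stated figure is miscalculated. It does not remove the mismatch between a statement about all patients and a schedule that allows less.

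A reader might infer several stronger things that the documents do not support:

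- **That the reporting periods are cut short.** They are not. Protocol 5.3.1 and 5.4.2.2 keep adverse event reporting open to 20 weeks or the last visit, whichever falls later. Pregnancies must be notified over the same period (5.4.3), and contraception is the patient's undertaking. Events in the gap may still reach the investigator. What is absent is a scheduled occasion to ask.
- **That the interval can be as short as 120 days.** Protocol 4.5.12.1 says the window for a rescheduled visit "may be extended to ± 4 days for Week 4 or ± 6 days". Using 6 days gives 476 − 14 − (336 + 6) = 120. But Protocol 4.3.2.1 sets dosing at ±5 days and omits a dose whose window is missed, and nothing says that the visit extension widens the dosing window. Appendix 1 prints N in place of a number for the dosing tolerance, so the passages should be reconciled. The 121-day figure does not need the extension.
- **That about half of completers fall short.** This would need visits to scatter evenly around target. The documents give no attendance distribution, and most early visits would miss day 140 by much less than 14 days.
- **That antibody or laboratory results at 18 weeks are inadequate.** The available text gives no half-life or washout figure from which to judge this.
- **That early-termination patients have no usable date.** Footnote c puts the termination visit 4 weeks after the last dose, and 16 further weeks can be inferred from SAP Section 2. Footnote e, read literally, still counts their follow-up windows from randomization. The text is unclear, not empty.

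**Conclusion.** The point holds in a limited form. For patients dosed through Week 50, the schedule allows the final visit 121 to 126 days after a late or on-time last dose at the early edge of the window, against 140 days in SAP Section 2. The consequences are an interval of up to 14 to 19 days with no planned contact while the reporting obligation is still running, and final safety samples taken that much earlier.

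This rests on three assumptions: footnote e applies to Weeks 50 and 70 alike, the last dose is given at the Week 50 visit within ±5 days, and the figures describe the permitted extreme, not the expected timing. Patients who stop drug early but keep to the schedule are followed for more than 20 weeks. No efficacy endpoint, sample size, power or type I error figure is affected. It is worth correcting because the remedy is small and the 20 weeks is stated for every patient, but it is not a threat to the trial's main conclusions.

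**What to change.** In Appendix 1, set the end-of-study visit no earlier than the later of Week 70 and 140 days after the actual last dose, with a one-sided window of 0 to +14 days. The later-of wording matters. Anchored on the last dose alone, a patient last dosed at Week 10 but still attending would have an end-of-study visit at Week 10 + 20 = Week 30. That is before Week 54 and at odds with the continued assessment on which the SAP 4.5.1 estimand relies. Under the later-of rule such patients keep their Week 54 and Week 70 visits.

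For patients who leave assessments through an early termination visit, count both safety follow-up visits from the last dose. This mirrors the main schedule: 62 − 50 = 12 weeks and 70 − 50 = 20 weeks (4 + 16). The second visit should carry the same one-sided window. The Week 62 window for other patients can stay.

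**Cost.** No visit, procedure or dosing rule is added or changed. The earliest visits move from day 126 or 121 after the last dose to day 140, which is 14 to 19 days later (about 2 to 3 weeks). With a last dose 5 days late, the latest permitted visit becomes 336 + 5 + 140 + 14 = day 495 from randomization, against day 490 now. The Week 70 exploratory endpoints (exacerbations through Week 70 and FEV₁ at Week 70) would then be assessed at or after the nominal date.
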